APPENDIX C. CLINICAL OPIATE WITHDRAWAL SCALE

Clinical Opiate Withdrawal Scale (COWS)

Daily Assessments Days -5 to 11/Follow-up (Morning and Evening during Residential Days -2 to 7, Morning Only Day 8/8a)

For each item, write in the number that best describes the patient's signs or symptoms. Rate on just the apparent relationship to opiate withdrawal. For example, if heart rate is increased because the patient was jogging just prior to assessment, the increased pulse rate would not add to the score.

Subject ID: _____	
Date: _____	Time: (eg, 15:00) 24-hour clock
Resting Pulse Rate: (record beats per minute) Measured after patient is sitting or lying for one minute 0 pulse rate 80 or below 1 pulse rate 81-100 2 pulse rate 101-120 4 pulse rate greater than 120	
Sweating: over past ½ hour not accounted for by room temperature or patient activity. 0 no report of chills or flushing 1 subjective report of chills or flushing 2 flushed or observable moistness on face 3 beads of sweat on brow or face 4 sweat streaming off face	
Restlessness Observation during assessment 0 able to sit still 1 reports difficulty sitting still, but is able to do so 3 frequent shifting or extraneous movements of legs/arms 5 Unable to sit still for more than a few seconds	
Pupil size 0 pupils pinned or normal size for room light 1 pupils possibly larger than normal for room light 2 pupils moderately dilated 5 pupils so dilated that only the rim of the iris is visible	
Bone or Joint aches If patient was having pain previously, only the additional component attributed to opiates withdrawal is scored 0 not present 1 mild diffuse discomfort 2 patient reports severe diffuse aching of joints/ muscles 4 patient is rubbing joints or muscles and is unable to sit still because of discomfort	

Runny nose or tearing Not accounted for by cold symptoms or allergies
 
0 not present 1 nasal stuffiness or unusually moist eyes 2 nose running or tearing 4 nose constantly running or tears streaming down cheeks
	

GI Upset: over last ½ hour
 
0 no GI symptoms 1 stomach cramps 2 nausea or loose stool 3 vomiting or diarrhea 5 multiple episodes of diarrhea or vomiting
	

Tremor observation of outstretched hands
 
0 no tremor 1 tremor can be felt, but not observed 2 slight tremor observable 4 gross tremor or muscle twitching
	

Yawning Observation during assessment
 
0 no yawning 1 yawning once or twice during assessment 2 yawning three or more times during assessment 4 yawning several times/minute
	

Anxiety or Irritability
 
0 none 1 patient reports increasing irritability or anxiousness 2 patient obviously irritable or anxious 4 patient so irritable or anxious that participation in the assessment is difficult
	

Gooseflesh skin
 
0 skin is smooth 3 piloerection of skin can be felt or hairs standing up on arms 5 prominent piloerection
	

Total score :
 
The total score is the sum of all 11 items
	

Rater Initials:
	

Score:
5-12 = mild;
13-24 = moderate;
25-36 = moderately severe;
More than 36 = severe withdrawal

Clinical Opiate Withdrawal Scale (COWS)

Clinical Testing Sessions (Days 1/1a-7)

Note: Day 14 session is paired with VIVITROL injection and only extends 60 min postdose.
 For each item, write in the number that best describes the patient's signs or symptoms. Rate on just the apparent relationship to opiate withdrawal. For example, if heart rate is increased because the patient was jogging just prior to assessment, the increased pulse rate would not add to the score.

Subject ID: _____ Date: _____	Predose	30 Min Postdose	60 Min Postdose	90 Min Postdose	120 Min Postdose	150 Min Postdose	180 Min Postdose
Time: (eg, 15:00) 24-hour clock							
Resting Pulse Rate: (record beats per minute) Measured after patient is sitting or lying for one minute 0 pulse rate 80 or below 1 pulse rate 81-100 2 pulse rate 101-120 4 pulse rate greater than 120							
Sweating: over past ½ hour not accounted for by room temperature or patient activity. 0 no report of chills or flushing 1 subjective report of chills or flushing 2 flushed or observable moistness on face 3 beads of sweat on brow or face 4 sweat streaming off face							
Restlessness Observation during assessment 0 able to sit still 1 reports difficulty sitting still, but is able to do so 3 frequent shifting or extraneous movements of legs/arms 5 Unable to sit still for more than a few seconds							
Pupil size 0 pupils pinned or normal size for room light 1 pupils possibly larger than normal for room light 2 pupils moderately dilated 5 pupils so dilated that only the rim of the iris is visible							
Bone or Joint aches If patient was having pain previously, only the additional component attributed to opiates withdrawal is scored 0 not present 1 mild diffuse discomfort 2 patient reports severe diffuse aching of joints/ muscles 4 patient is rubbing joints or muscles and is unable to sit still because of discomfort							

Runny nose or tearing Not accounted for by cold symptoms or allergies 0 not present 1 nasal stuffiness or unusually moist eyes 2 nose running or tearing 4 nose constantly running or tears streaming down cheeks							
GI Upset: over last ½ hour 0 no GI symptoms 1 stomach cramps 2 nausea or loose stool 3 vomiting or diarrhea 5 multiple episodes of diarrhea or vomiting							
Tremor observation of outstretched hands 0 no tremor 1 tremor can be felt, but not observed 2 slight tremor observable 4 gross tremor or muscle twitching							
Yawning Observation during assessment 0 no yawning 1 yawning once or twice during assessment 2 yawning three or more times during assessment 4 yawning several times/minute							
Anxiety or Irritability 0 none 1 patient reports increasing irritability or anxiousness 2 patient obviously irritable or anxious 4 patient so irritable or anxious that participation in the assessment is difficult							
Gooseflesh skin 0 skin is smooth 3 piloerection of skin can be felt or hairs standing up on arms 5 prominent piloerection							
Total scores The total score is the sum of all 11 items							
Rater Initials							

Score:
5-12 = mild;
13-24 = moderate;
25-36 = moderately severe;
More than 36 = severe withdrawal

Clinical Opiate Withdrawal Scale (COWS)

Day 8/8a – Naloxone Challenge/VIVITROL Injection

For each item, write in the number that best describes the patient's signs or symptoms. Rate on just the apparent relationship to opiate withdrawal. For example, if heart rate is increased because the patient was jogging just prior to assessment, the increased pulse rate would not add to the score.

Subject ID: _____ Date: _____	Challenge, Part 1		Challenge, Part 2			
	Pre-dose	10 Min Postdose Part 1	20 Min Postdose Part 1	10 Min Postdose Part 2	20 Min Postdose Part 2	1 Hour Postdose VIVITROL
Times: (eg, 15:00) 24-hour clock						
Resting Pulse Rate: (record beats per minute) Measured after patient is sitting or lying for one minute 0 pulse rate 80 or below 1 pulse rate 81-100 2 pulse rate 101-120 4 pulse rate greater than 120						
Sweating: over past ½ hour not accounted for by room temperature or patient activity. 0 no report of chills or flushing 1 subjective report of chills or flushing 2 flushed or observable moistness on face 3 beads of sweat on brow or face 4 sweat streaming off face						
Restlessness Observation during assessment 0 able to sit still 1 reports difficulty sitting still, but is able to do so 3 frequent shifting or extraneous movements of legs/arms 5 Unable to sit still for more than a few seconds						
Pupil size 0 pupils pinned or normal size for room light 1 pupils possibly larger than normal for room light 2 pupils moderately dilated 5 pupils so dilated that only the rim of the iris is visible						
Bone or Joint aches If patient was having pain previously, only the additional component attributed to opiates withdrawal is scored 0 not present 1 mild diffuse discomfort 2 patient reports severe diffuse aching of joints/ muscles 4 patient is rubbing joints or muscles and is unable to sit still because of discomfort						

Runny nose or tearing Not accounted for by cold symptoms or allergies
 
0 not present 1 nasal stuffiness or unusually moist eyes 2 nose running or tearing 4 nose constantly running or tears streaming down cheeks
						

GI Upset: over last ½ hour
 
0 no GI symptoms 1 stomach cramps 2 nausea or loose stool 3 vomiting or diarrhea 5 multiple episodes of diarrhea or vomiting
						

Tremor observation of outstretched hands
 
0 no tremor 1 tremor can be felt, but not observed 2 slight tremor observable 4 gross tremor or muscle twitching
						

Yawning Observation during assessment
 
0 no yawning 1 yawning once or twice during assessment 2 yawning three or more times during assessment 4 yawning several times/minute
						

Anxiety or Irritability
 
0 none 1 patient reports increasing irritability or anxiousness 2 patient obviously irritable or anxious 4 patient so irritable or anxious that participation in the assessment is difficult
						

Gooseflesh skin
 
0 skin is smooth 3 piloerection of skin can be felt or hairs standing up on arms 5 prominent piloerection
						

Total scores
 
The total score is the sum of all 11 items
						

Rater Initials
						

Same rater as previous? (Y/N)
	N/A					

Score:
5-12 = mild;
13-24 = moderate;
25-36 = moderately severe;
More than 36 = severe withdrawal

APPENDIX D. SUBJECTIVE OPIATE WITHDRAWAL SCALE

ALKERMES ALK6428-A302

Subject Initials:	Site No. / Subject ID No.	Date of Assessment (DD/MMM/YYYY)	Time Performed (24 hours)
		_ / _ / _	_ : _

SOWS

Instructions: Please complete a survey each evening.

Answer the following statements as accurately as you can, circling the answer that best fits the way you feel now.

- 0 = not at all
- 1 = a little
- 2 = moderately
- 3 = quite a bit
- 4 = extremely

[figure not shown]
		Not at all	A little	Moderately	Quite a bit	Extremely
1	I feel anxious.	0	1	2	3	4
2	I feel like yawning.	0	1	2	3	4
3	I'm perspiring.	0	1	2	3	4
4	My eyes are tearing.	0	1	2	3	4
5	My nose is running.	0	1	2	3	4
6	I have goose flesh.	0	1	2	3	4
7	I am shaking.	0	1	2	3	4
8	I have hot flashes.	0	1	2	3	4
9	I have cold flashes.	0	1	2	3	4
10	My bones and muscles ache.	0	1	2	3	4
11	I feel restless.	0	1	2	3	4
12	I feel lightheaded.	0	1	2	3	4
13	I feel like vomiting.	0	1	2	3	4
14	My muscles twitch.	0	1	2	3	4
15	I have cramps in my stomach.	0	1	2	3	4
16	I feel like shooting up now.	0	1	2	3	4

APPENDIX E. DESIRE FOR OPIOIDS VISUAL ANALOGUE SCALE

[figure not shown]
Desire for Opioids VAS

Instructions: Below is a question regarding your desire for opioids. We would like to know how strong your desire for opioids has been over the past 24 hours. Please place a vertical line (|) somewhere on the line between **0** and **100** to indicate how strong your desire for opioids has been over the past 24 hours.

Correct:

[figure not shown]
Incorrect:

If you make a mistake, cross out your answer, initial and date it, and place a new vertical mark on the line.

Please indicate how strong your desire for opioids has been over the past 24 hours below:

**Your own
desire for
opioids**

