8.4. Withdrawal Assessments Throughout the Residential Period

Every morning (AM) and every evening (PM) during the residential period (Days -2 to 8/8a) subjects will undergo a basic withdrawal evaluation consisting of COWS, SOWS, VAS, and vital signs ([Figure 2](#)). The AM assessments should be conducted first thing in the morning and ≥ 60 minutes prior to the baseline assessments. On Day 8/8a, the COWS/SOWS conducted as part of the AM assessments can serve as the pre-naloxone challenge COWS/SOWS if they are administered within an hour (≤ 60 minutes) prior to the initial administration of naloxone in Part 1 of the naloxone challenge. The PM assessments should be conducted in the evening. In the event that they cannot be conducted in the evening, the earliest they can be completed is at 60 minutes after the 120-minute post-first NTX/PBO-N dose for early qualifiers, and at 60 minutes after the 180-minute post-first NTX/PBO-N dose for late qualifiers. The 60-minute post-VIVITROL injection assessments on Day 8/8a can serve as the PM assessments for those days.

In the event that a subject is admitted for the residential stay early (on Days -5, -4 or -3), standard AM and PM assessments should be conducted. For subjects who remain on the residential unit for clinical stabilization on BUP, these study assessments are not required.

On Days 1/1a to 7, subjects will undergo daily clinical testing to measure opioid withdrawal effects in response to study drug dosing. These clinical testing sessions will include the following assessments (see [Section 8.8](#) for more details on individual assessments):

- Vital signs (body temperature, respiration rate, heart rate, systolic and diastolic blood pressure)
- Oxygen saturation
- Pupillometry
- COWS
- SOWS
- VAS

A timetable for clinical testing sessions is provided in [Figure 2](#). On Days 1/1a to 7, clinical testing sessions will begin approximately 15 minutes prior to the first dose of naltrexone or

PBO-N and will last at least 120 minutes following the first dose (60 minutes following the second dose). Clinical testing may potentially last 180 minutes for late qualifying subjects who receive the second naltrexone or PBO-N dose at the 120-minute timepoint (see [Section 8.2.2](#) for more information regarding early and late qualification). A window of +30 minutes is allowed for these assessments.

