- ^f In addition to the study assessments conducted during the clinical testing sessions, vital signs will be measured each morning and evening throughout the residential period (Days -2 to 8/8a and any additional residential days, in the case of earlier admission or later discharge). Vital signs (blood pressure, heart rate, respiratory rate and body temperature) will be measured after the subject has been in a seated position for at least 5 minutes. In addition to standard vital sign measurements, clinical testing sessions on Days 1/1a to 7 will include oxygen saturation and pupillometry measurements to assess withdrawal effects in response to drug dosing. Measurements will be collected pre- and postdose as indicated in [Figure 2](#). Details regarding the timing of these assessments are provided in [Section 8.4](#).
- ^g A urine drug screen will be performed at all specified timepoints. The urine drug screen should be performed in the morning. On Days 1/1a to 7, it should be performed prior to the clinical testing sessions.
- ^h Eligibility will be confirmed prior to randomization and administration of the first dose of NTX/PBO-N.
- ⁱ Subjects not qualifying for randomization on Day 1 will receive the Day -1 BUP dose and will not receive NTX/PBO-N. Subjects not qualifying for VIVITROL on Day 8 will receive the Day 7 NTX/PBO-N dose, along with the COWS conducted for clinical safety purposes only.
- ^j Standing ancillary medication regimen begins on Day -2. In the event that a subject is admitted for the residential stay early (on Days -5, -4, or -3), the ancillary medication regimen will begin as soon as the subject becomes residential. Also, if needed for AE treatment or prophylaxis, ancillary medications may be initiated at the clinician's discretion on or after Day -5.
- ^k For subjects receiving VIVITROL on Day 8/8a, ancillary medications will be reduced as indicated in [Table 6](#).
- ^l COWS, SOWS and VAS to be recorded each morning (AM) and evening (PM) throughout the residential period (Days -2 to 8/8a) and any additional residential days, in the case of earlier admission or later discharge. On Days 1/1a to 7 the COWS, SOWS and VAS will also be administered as part of clinical testing sessions to measure withdrawal effects in response to study drug dosing. Details regarding the timing of these assessments are provided in [Section 8.4](#).

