8.8.11.7. Desire for Opioids Visual Analogue Scale

The desire for opioids will be measured using a 100-mm, horizontal VAS, with 0 anchored on the left representing "no desire for opioids" and 100 anchored on the right representing "strongest imaginable desire for opioids." Subjects will place a vertical line on the scale to indicate their desire for opioids at that particular time. The VAS will be self-administered at the timepoints specified in Table 4. In addition to morning and evening assessments throughout the residential period, the VAS will be self-administered during clinical testing sessions (see

Section 8.4) according to the timetable provided in [Figure 2](#). A sample can be found in [Appendix E](#).

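### Section 8.8.11.7 defines the desire-for-opioids VAS as a momentary rating, but its only form, Appendix E, asks about the past 24 hours

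*Protocol*

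**What the plan says.** Section 8.8.11.7 describes a self-administered 100-mm line and states the time frame: "Subjects will place a vertical line on the scale to indicate their desire for opioids at that particular time". It refers the reader to Appendix E for a sample of the form. On frequency it adds: "In addition to morning and evening assessments throughout the residential period, the VAS will be self-administered during clinical testing sessions".

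Section 8.4 gives the purpose of the Days 1/1a-7 sessions: "subjects will undergo daily clinical testing to measure opioid withdrawal effects in response to study drug dosing". The footnote to Table 4 in Section 8.7 applies that purpose to this scale: "VAS will also be administered as part of clinical testing sessions to measure withdrawal effects in response to study drug dosing". Section 8.4 also schedules the VAS on Day 8/8a before the VIVITROL injection and 30 and 60 minutes after it. Table 4 has one VAS visit per day on Days 9, 10 and 11.

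Appendix E instructs the subject: "We would like to know how strong your desire for opioids has been over the past 24 hours". The prompt at the point of marking repeats the period: "Please indicate how strong your desire for opioids has been over the past 24 hours below".

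Section 13.4.3 lists the mean VAS score over Days 1/1a-11 as an other secondary endpoint, analysed by ANOVA with treatment as a factor.

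**The concern.** The text and the form ask for different quantities, and no part of the protocol chooses between them. Because the scale is self-administered, the subject answers the printed question. The planned schedule (morning, evening, several times around each dose, and twice within an hour after VIVITROL) makes sense only for a rating of the moment. With a 24-hour recall, ratings taken minutes apart look back on almost the same day.

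At stake is what the data mean. A statistical analysis plan cannot recover momentary desire from answers about the last day. Sites that explain the scale as Section 8.8.11.7 does, and sites that simply hand over the form, could also collect different things under one endpoint name.

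**Working it through.** The plan gives no figure to reproduce here, so the check compares the texts and then works out how far the recall periods overlap at the scheduled times.

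**Side by side**
- Section 8.8.11.7: desire at the time of marking.
- Appendix E: desire over 24 hours, stated in the instruction and again in the response prompt.
- Appendix D (SOWS), given at the same sessions, asks how the subject feels now.
- Appendix C (COWS) has separate forms for daily use, dosing sessions and Day 8/8a. The VAS has one form for all settings.

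**Inputs**
- Recall period: 24 h (Appendix E).
- Session start: "clinical testing sessions will begin approximately 15 minutes prior to the first dose" (Section 8.4). The 15 minutes are taken as exact below, although the text says approximately.
- Longest session: "Clinical testing may potentially last 180 minutes for late qualifying subjects", with a +30 minute assessment window (Section 8.4).
- Day 8/8a: ratings 30 and 60 minutes after injection (Section 8.4).

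**Day 8/8a: share of the recall period before the injection** = (24 − t)/24
- t = 0.5 h: 23.5/24 = 98%.
- t = 1 h: 23/24 = 96%.

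**Days 1/1a-7: recall shared by two ratings in one session** = (24 − gap)/24
- Largest gap: 15 + 180 + 30 = 225 min = 3.75 h, so 20.25/24 = 84%.
- Largest gap without the +30 minute window: 195 min = 3.25 h, so 20.75/24 = 86%.
- Ratings 30 min apart: 23.5/24 = 98%.

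**First dosing day: share of the recall period before the first dose** = (24 − t)/24
- t = 2 h: 22/24 = 92%.
- t = 3 h: 21/24 = 88%.
- t = 3.5 h (180 min plus the window): 20.5/24 = 85%.

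So the session ratings on that day mostly recall pretreatment time.

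**What one rating would show.** Assume desire is constant before the injection, changes by D at the injection and stays there. At 60 minutes a momentary rating shows all of D. The form does not say whether to report an average or the worst moment:
- Average recall: (1/24) × D, or 4% of D.
- Worst moment, desire rises: the new level is the 24-hour peak, so 100% of D.
- Worst moment, desire falls: the earlier peak is still inside the 24 hours, so 0% of D.

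The range is therefore 0% to 100%.

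**The case against.** Several points on the other side are sound.

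- **Appendix E is called a sample.** Other sample forms carry unadapted text: a COWS form for Days 1/1a-7 mentions a Day 14 session, and the SOWS form asks for completion each evening. The 24-hour wording may be left over from a template, with Section 8.8.11.7 stating the intent. That is plausible and makes this a form-alignment error. It does not remove the error, because no other VAS form is shown.
- **The overlap figures concern change within a session, and no such VAS analysis is planned.** This stands. The one VAS endpoint in Section 13.4.3 is a mean over about 11 days, and the overlap of ratings 30 minutes apart says little about a group comparison of that mean.
- **Both blinded arms use the same form.** This stands: no differential bias between the arms is shown.

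A reader might infer that none of the post-VIVITROL ratings can show response to treatment. The documents do not support that. On Days 9-11 there is one rating per day, and its 24-hour period falls largely or wholly after the injection. Nor is it right that session and Day 8/8a ratings can show nothing: under worst-moment recall, a rise above the previous 24-hour peak would show in full. A reader might also infer that the group difference in mean VAS is biased in a known direction. It could be diluted under average recall, inflated if brief peaks are carried into later ratings, or little changed if the effect is sustained. The protocol gives no basis for choosing among these.

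**Conclusion.** The protocol is wrong as written: its body and its form contradict each other on the recall period. This is an inconsistency, not a questionable design choice. If the form is used as printed, the Days 1/1a-7 session ratings and the 30- and 60-minute ratings on Day 8/8a would poorly reflect response to dosing. The mean VAS over Days 1/1a-11 would not measure the quantity defined in Section 8.8.11.7, and part of its first-day input would be mostly pretreatment recall.

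This rests on the printed form being the one used and on subjects answering it literally. The 84% figure also treats the approximate 15-minute predose start as exact. The reach is one secondary endpoint that is not key. The primary endpoint, key secondary endpoint and sample size do not depend on the VAS. The point should be corrected, but it does not threaten the trial's main conclusion.

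**What to change.** Before data collection, reword both the instruction and the response prompt in Appendix E to ask for desire right now, so that they match Section 8.8.11.7. Use that wording for every rating that enters the Days 1/1a-11 mean, including the outpatient visits on Days 9-11, so that the mean does not mix two recall periods. The cost is one reworded form. No assessment is added, and the visit schedule, dosing, sample size and planned analysis stay as they are.
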